#### 9.2.15 RANDOMIZATION (DAY 0)

According to an intention-to-treat (ITT) methodology, randomization will be performed upfront, before any further invasive tumor assessment (angiogram) or treatment planning.

Patients will be randomized 1:1 to study treatment, either the Control arm or the Treatment arm.

If a patient is determined to be eligible to participate in the trial, the study site will contact the central randomization office via telephone or by internet where randomization will be determined using assignment by a computer-generated randomization scheme. Upon randomization, each patient will be assigned a subject identity code consisting of the protocol number, the site number (e.g. 01) and a patient identifier number (e.g. 001).

In order to create a balance between study arms, patients will be stratified at randomization based on the following:

- AFP ≤ 400 ng/mL or >400 ng/mL
- Participating trial site

Although this will not be considered as stratification criteria upfront, each patient will be registered as naïve or recurrent, i.e. whether or not the HCC diagnosis presents at first diagnosis, with no previous treatment, or as a recurrent tumor.

Patients randomized to the Control arm or the Treatment arm, unable to receive their planned study treatment, will continue to be followed under their assigned study arm for the purpose of the intent-to-treat analysis.

Patients who do not meet the eligibility criteria should not be randomized and the reason for treatment ineligibility should be documented on the Screen Failure Log.

#### 9.2.16 STUDY TREATMENTS

#### 9.2.16.1 THERASPHERE

TheraSphere will be administered to all disease present at randomization.

#### 9.2.16.1.1 RE-TREATMENT

Patients can receive a subsequent TheraSphere administration in the absence of radiological progression criteria at investigator discretion. During follow-up, for patients in the Treatment arm who have demonstrated hepatic progression with hepatic lesions amenable to TheraSphere., re-treatment with TheraSphere is allowed. Any re-treatment should take place at least 28 days from the last TheraSphere treatment.

Patients must meet initial eligibility criteria for TheraSphere treatment (Section 8.1) to receive subsequent treatments. A maximum of three (3) TheraSphere administrations are permitted in total.

Patients will undergo additional pre-treatment evaluations as described in Section 9.2.16.1.2 at the investigator's discretion prior to administration of subsequent TheraSphere treatments to assess and address any changes in extra-hepatic shunting that may have developed.

#### 9.2.16.1.2 THERASPHERE PRE-TREATMENT EVALUATION

Patients randomized to the Treatment arm must undergo the following evaluations to determine eligibility to receive the TheraSphere. These include:

- Hepatic Angiography: selective celiac and superior mesenteric arteriograms are needed to evaluate the hepatic arterial anatomy for the whole liver, as well as evaluation of potential sources of extrahepatic blood supply to tumors. The goal is to identify, within the hepatic vascular anatomy, a catheter placement location that allows a single TS infusion throughout the lobar tumor volume without administration of microspheres to extra-hepatic structures.
- A technetium-99m macroaggregated albumin (99mTc-MAA) scan is used to assess the potential for shunting microspheres to the lungs as well as the potential for the deposition of microspheres to the gastrointestinal (GI) tract. Repeat 99mTc-MAA may be needed for subsequent treatments to estimate cumulative lung shunt or re-asses GI flow. Note that 3 technical factors (time between administration of 99mTc-MAA and the scan, 99mTc-MAA particle size and the presence of free 99mTc-MAA) can lead to an over-estimation of shunting to the lungs.

TheraSphere should not be administered to a patient randomized to the Treatment arm if:

- Deposition of microspheres to the GI tract that cannot be corrected by placement of the catheter distal to collateral vessels or the application of standard angiographic techniques, such as coil embolization to prevent deposition of microspheres in the GI tract.
- Exposure of radiation to the lungs of 30 Gray (Gy) for a single infusion or a cumulative 50 Gy limit for all infusions of TheraSphere that cannot be corrected by dose reduction of TheraSphere.

In the event that a patient randomized to the TheraSphere arm is determined not to be suitable for and/or cannot be safely treated with TheraSphere, that patient will not receive TheraSphere and may proceed to treatment with SOC sorafenib regimen as described in Section 9.2.16.2.

#### 9.2.16.1.3 THERASPHERE ADMINISTRATION STRATEGY

For patients eligible to receive TheraSphere, the administration strategy (choice of artery position to infuse the target vascular bed; selection of placement of coil embolization or other techniques used to prevent microsphere deposition to the GI tract) should be determined. Dosimetry is based on the volume of the target vascular bed supplied by the artery selected for infusion. Patients requiring coil embolization to prevent microsphere disposition to the GI tract should undergo this procedure during TheraSphere work-up.

Since the treatment approach for Y90 is lobar, proper imaging and volume calculation is essential for dosimetry purposes. The ability to understand hepatic anatomy relies on the sound understanding of the Couinaud hepatic segments 21. Anatomically, the middle hepatic vein separates the right and left lobes. When drawing regions of interest and calculating lobar volumes, it is the middle hepatic vein that should be used as the anatomic delineator between the right and left lobes. If the middle hepatic vein cannot be seen, then the gallbladder and its axis relative to the liver can be used. This technique assumes standard arterial anatomy with single right and left hepatic arteries. If variants are observed angiographically, for example, an accessory right hepatic artery, then accurate angiographic correlations must be performed when drawing the regions of interest for lobar or segmental lobar volumes. This will ensure that accurate volumes are obtained and 3 or more infusions are administered. The volume that needs to be used for Y90 dosimetry is that volume of liver that is perfused by the vessel that will be infused.

Arterial redistribution techniques are permitted for intra-tumoral and/or less than one liver segment.

Target liver mass is determined by the positioning of the delivery catheter in the hepatic vasculature and the resulting liver area (segments) infused. Since there is considerable individual variation in hepatic vascular anatomy, the determination of target liver mass will depend on the variant encountered. The Table below presents the most commonly encountered variants with the corresponding segments associated to them.

# STANDARD AND VARIANT HEPATIC VASCULAR ANATOMY AND CORRESPONDING COUINAUD SEGMENTS

Hepatic Vascular Anatomya: Angiographic Findings	Target Segments – Infusion 1 b,c	Target Segments – Infusion 2	Target Segments – Additional Infusion
Standard right and left hepatic arteries	1, 5, 6, 7, 8	2, 3, 4	
Replaced right hepatic with flow to medial segment left lobe	1, 4, 5, 6, 7, 8	2, 3	
Replaced right hepatic artery without flow to middle lobe, left hepatic artery with flow to medial and lateral segments left lobe	1, 5, 6, 7, 8	2, 3, 4	
Replaced left hepatic artery without flow to medial lobe	1, 4, 5, 6, 7, 8	2, 3	
Replaced left hepatic artery with flow to medial lobe	1, 5, 6, 7, 8	2, 3, 4	
Accessory right hepatic artery	6, 7	2, 3, 4	1, 5, 8
Right hepatic artery in the presence of an accessory right hepatic	5, 8	2, 3, 4	1, 6, 7
Middle hepatic artery (irrespective of origin)	1, 5,6, 7, 8	4	2, 3

#### Notes:

- a) vascular anatomy subject to variation
- b) assumes caudate lobe (segment 1) derives blood supply from right hepatic artery
- c) caudate lobe (segment 1), right anterior lobe (segments 5/8), right posterior lobe

(segments 6/7), left medial lobe (4), left lateral lobe (2, 3)

#### 9.2.16.1.4 THERASPHERE DOSE DETERMINATION

The screening angiogram and  $^{99m}$ TC-MAA scan are used to determine lobar liver volume from CT or MR images, to identify vascular shunting to the gastrointestinal tract requiring use of angiographic occlusion techniques and to determine the lung shunt fraction. Patients will receive TheraSphere at a dose consistent with the approved product label. The target dose is 120 Gy  $\pm$  10%. Dose reduction is permitted when required to ensure radiation exposure to the lung is less than 30 Gy for a single treatment or 50 Gy cumulative. Dose reduction below 80 Gy per treatment is not permitted.

Calculation of Lung Shunt Factor: Lung shunt factor is determined from the 99mTc-MAA scan using the following equation: Lung shunt Fraction (F) = total lung counts/(total lung+ liver counts)

Calculation of Target Liver Mass: Convert the target liver volume to mass assuming a conversion factor of 1.03g/cm^3.

#### Calculation of Activity required to deliver a desired dose of 120 Gy:

The amount of radioactivity required to deliver a desired target dose (120 Gy) to the selected liver target, adjusted for the estimated fraction that will be shunted to the lung, is calculated using the following formula:

# Activity Required (GBq) = [Desired Dose (Gy)] [Mass of Selected Liver Target (kg)][1+F] 50

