#### 9.2.16.1.8 THERASPHERE ADMINISTRATION DOCUMENTATION

Any technical problems or complications related to the delivery of TheraSphere treatment to the patient must be documented in the medical record. The details of any event and its impact on the patient should be documented on an Adverse Event eCRF. Patients in the Treatment arm must certify continued eligibility prior to administration of TheraSphere. A new blood draw for labs and pregnancy and an ECOG Performance Status test may be performed within 7 days before TheraSphere administration at physician discretion to confirm baseline results.

Using institutional practices, the activity of each vial of TheraSphere will be determined prior to administration. This activity will be used to calculate the actual dose delivered to the liver and lung which will be recorded on the appropriate eCRF.

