#### Calculation of the liver dose (Gy) delivered:

Calculation of the delivered dose per infusion takes into account the activity lost to lung shunting plus activity associated with residual microspheres in the administration system and is provided by the following formula:

> 50[Injected Activity (GBq)][1-F][1-R] Dose (Gy) = Mass of Selected Liver Target (kg)

where F = lung shunt fraction (determined in Section 9.2.14.1.3)

R = residual activity fraction

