# 14 Protocol Deviations

It is vital to the success of the study that the investigator adheres to the details of the protocol. All deviations from the protocol must be approved by the sponsor before implementation.

Protocol deviations will be tracked according to the following categories:

- 1. Informed Consent process not followed
- 2. Screening tests or procedures out of window or not done
- 3. Imaging tests not performed as required
- Inclusion/Exclusion criteria violation
- TheraSphere dose delivery outside range of 80 to 150 Gy
- 6. Lung dose exceeds 30 Gy single treatment, 50 Gy cumulative
- 7. Study visits, tests or procedures conducted out of window or not done
- Liver-directed treatment of HCC other than TheraSphere

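### The TheraSphere activity-planning formula and the delivered-dose formula are not inverses, so an 80 Gy plan injected exactly as calculated computes below 80 Gy and is tracked as a deviation

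*Protocol*

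**What the plan says.** **Planning.** Protocol 9.2.16.1.4 defines the lung shunt fraction F as "total lung counts/(total lung+ liver counts"). The activity for a desired dose is "Activity Required (GBq) = [Desired Dose (Gy)] [Mass of Selected Liver Target (kg)][1+F] 50", described as "adjusted for the estimated fraction that will be shunted to the lung". The next calculation, estimated lung exposure, assigns the fraction F of that calculated activity to the lung.

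**Scoring.** Under 9.2.16.1.8, "the activity of each vial of TheraSphere will be determined prior to administration", and that measured activity is the basis of the recorded dose. The liver dose is "50[Injected Activity (GBq)][1-F][1-R] Dose (Gy) = Mass of Selected Liver Target (kg"). The protocol says this "takes into account the activity lost to lung shunting plus activity associated with residual microspheres in the administration system". R comes from dose-rate measurements on the waste container after the infusion.

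**Limits.** For the lower limit, 9.2.16.1.4 states "Dose reduction below 80 Gy per treatment is not permitted", with no tolerance. The Synopsis and 9.2.16.1.7 give the minimum as 80 Gy with a 10% tolerance either way. Section 14 lists as a tracked deviation "TheraSphere dose delivery outside range of 80 to 150 Gy", again with no tolerance. Reduction is allowed in order to keep lung exposure within 30 Gy per treatment and 50 Gy cumulative.

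**The concern.** A planning equation that claims to adjust for lung shunt should, with no residual, return the planned dose when its activity is put into the scoring equation. This pair does not. Multiplying by (1+F) does not undo multiplication by (1-F). The planning section is also inconsistent within itself: its lung-exposure formula sends F of the activity to the lung, which leaves 1-F for the liver.

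The gap grows with F, and F is above zero in any patient whose dose is reduced for lung exposure. These are the patients planned near the floor. A site could follow 9.2.16.1.4 exactly and still record a Section 14 dose deviation. SAP 8.2 summarises deviations by category and arm, and SAP 8.10.1.1 summarises delivered lobar dose. Both summaries would then mix a formula effect with real under-delivery.

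**Working it through.** **Inputs.** D is the planned dose (120 Gy target, 80 Gy floor). M is the target liver mass; 1.3 kg is taken from the worked example in SAP 6.5.1.1. The documents give no distribution for F or R, so the values below are assumptions. The only shunt percentage stated is 20%, and it applies to prior radioembolization in the eligibility criteria.

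**Round trip.**

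1. Planning: A = D × M × (1+F) / 50.
2. Scoring: delivered = 50 × A_injected × (1-F) × (1-R) / M.
3. With A_injected = A: delivered = D × (1+F)(1-F)(1-R) = D × (1-F²)(1-R). M cancels.

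The stated 120 Gy is reproduced exactly at F = R = 0. Otherwise:

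| F | R | Planned 120 Gy | Planned 80 Gy |
|---|---|---|---|
| 0.05 | 0 | 119.7 | 79.8 |
| 0.10 | 0 | 118.8 | 79.2 |
| 0.20 | 0 | 115.2 | 76.8 |
| 0.10 | 0.03 | 115.2 | 76.8 |
| 0.20 | 0.03 | 111.7 | 74.5 |

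The rows with R = 0 isolate the formula mismatch, which is F²: 1% at F = 0.10 and 4% at F = 0.20. At F = 0.10, a residual of 0.03 costs more than the mismatch does.

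**How large F can be.** Planned lung dose = 50 × A × F = D × M × F × (1+F). Setting this to 30 Gy with M = 1.3 kg:

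- D = 120: 156 × F(1+F) = 30, so F = 0.165. Delivered at R = 0 is 120 × (1-0.165²) = 116.7 Gy, inside 120 ± 10%.
- D = 80: 104 × F(1+F) = 30, so F = 0.234. Delivered at R = 0 is 80 × (1-0.234²) = 75.6 Gy. With R = 0.03 it is 73.4 Gy.

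**Against the limits.** All the 80 Gy results above fall below 80, so Section 14 counts them. All lie within 72 to 88 Gy, the tolerance in the Synopsis and 9.2.16.1.7. Adopting that tolerance would not align the formulas: a 72 Gy plan at F = 0.20 and R = 0 computes to 72 × 0.96 = 69.1 Gy.

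**Effect of vial activity.** The scored dose reaches D if injected activity exceeds calculated activity by the factor 1/((1-F²)(1-R)). At F = 0.20 this is 1.042 with R = 0 and 1.074 with R = 0.03. With the 64.1 h half-life in Section 5.1, a factor of 1.074 corresponds to about 6.6 h of decay.

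**The case against.** **Vial activity.** A reader might infer that delivered dose always falls below plan and that every plan at the floor becomes a deviation. The documents do not support that. Scoring uses measured vial activity, and vial choice and decay timing (9.2.16.1.5) can put it above or below the calculated value by several percent. The shortfall is certain only when injected equals calculated activity and F or R is above zero. This objection stands. Even so, no rule in the protocol tells sites to offset the mismatch.

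**Residual.** A reader might also fault planning for leaving out R. R is measured after infusion, so its actual value cannot enter the plan. A residual shortfall is real under-delivery, and the scoring formula is meant to capture it. Only the F² part is a formula inconsistency.

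**Size.** Large gaps need large F, and the lung limit restricts that. At 120 Gy and F = 0.30 the lung dose is 120 × 0.30 × 1.30 = 46.8 Gy per kg, so the case arises only below 30/46.8 = 0.64 kg. A 120 Gy plan would score below 80 Gy only if (1-F²)(1-R) were under 0.667, so full-dose patients are essentially untouched by the lower deviation limit.

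**The tolerance conflict.** It can be said that these cases are deviations only because Section 14 has no tolerance at 80 Gy. That is a related conflict and should be settled at the same time. It is not the same one, because the formulas disagree whichever floor is used.

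**Consequences.** Dose is not among the major violations in Section 15, although Section 10.2.1 points to Section 14 for violations that remove patients from the per-protocol set. SAP 8.3 defines no per-protocol population, and SAP 8.9 analyses efficacy in the Treated Population. Nothing in the SAP says that its summary of whether the dose was given as intended is derived from the delivered-dose formula. These points stand and limit what is at stake.

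**Conclusion.** The two formulas are inconsistent as written, and that rests on algebra alone. If injected activity equals calculated activity, the scored dose before residual is D(1-F²), which is 1% below plan at F = 0.10 and 4% below at F = 0.20. Both F values are assumed. The practical effect is concentrated near the floor, as in the 75.6 Gy example, which assumes a 1.3 kg target, a lung dose at the 30 Gy limit and no residual. There, a site that followed the planning rules can be recorded as deviating.

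A reader might take this as evidence of systematic under-dosing or as a threat to the survival comparison. Neither follows. The documents give no F or R values and no injected activities for patients, and no efficacy analysis depends on the dose category. What is affected is the meaning of the reported dose and of the dose-deviation counts.

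**What to change.** **Protocol text.** The sponsor must reconcile 9.2.16.1.4 (dose determination, activity and lung-exposure calculations), 9.2.16.1.7, the delivered-dose calculation in 9.2.16.1.8 and Section 14, so that planned and delivered dose rest on one stated basis. The text should say whether the 80 Gy floor and the 80 to 150 Gy range refer to planned or delivered dose, and the Synopsis should agree with it. The activity and lung-exposure formulas are linked, so they need to be considered together. No view is taken here on which formula, dose or limit is right.

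**Reporting.** SAP Section 5 records that the study was terminated early, so the practical step is in the analysis:

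- Show planned and delivered dose side by side.
- Where F and R can be retrieved, separate the (1-F²) formula component from residual R. Section 9.2.16.1.8 says the delivered liver and lung doses are recorded on the eCRF. It does not say that F and R are, so this must be confirmed first.
- Flag dose deviations explained by the formula mismatch alone, and keep them in the counts.

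**Cost.** A small amount of extra derivation, and slightly changed dose and deviation summaries. The reporting step changes no patient's care and no efficacy analysis.

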## Calculation of estimated lung radiation exposure (Gy):

[figure not shown]
Lung Dose (Gy) per infusion = 50 \* Calculated Activity in gigabecquerel (GBq) \* F

Cumulative exposure is the sum of estimated exposure per infusion for all planned infusions.

#### 9.2.16.1.5 THERASPHERE DOSE VIAL SELECTION

Selection of the dose vial size to supply the required activity (GBq) for delivery of the desired target dose to the selected target liver volume via the selected vascular route is dependent on the day and time of the scheduled patient treatment and must account for the time zone in which the hospital is located and the decay in radioactivity over time. The impact of time for available dose sizes is illustrated in the decay curve below.

The TheraSphere Treatment Window Illustrator can be used to select the appropriate dose vial or combination of dose vial(s) required to deliver the calculated activity required.

Note: The number of microspheres does not change over time.

#### 9.2.16.1.6 THERASPHERE ORDERING

Orders must be placed using the order form provided by the sponsor. Standard dose vial sizes (3 GBq, 5 GBq, 7 GBq, 10 GBq, 15 GBq and 20 GBq) are made to stock and can be ordered at anytime. Orders for custom size dose vials must be received at TheraSphere Customer Service by 12 noon Eastern Time on the Tuesday before the desired Calibration Date (approximately Day 7-10 post-randomization). TheraSphere will be delivered to the institution's designated radiopharmacy and handled according to institutional practices.

Each vial of TheraSphere will be shipped with a packing slip, a copy of which must be transferred to the study coordinator for device accountability so that the vials used can be tracked to the specific infusion(s) for each patient. Disposal of used or any unused vials will be handled in accordance with hospital standard practices for disposal of radioactive materials.

#### 9.2.16.1.7 THERASPHERE ADMINISTRATION

TheraSphere will be administered at a dose consistent with the approved product label. A target dose of 120  $\pm$  10% Gy to the target liver tissue is recommended. Dose reduction to a minimum dose of 80  $\pm$  10% Gy is permitted to manage radiation exposure to the lungs within the limits of 30 Gy for a single infusion and 50 Gy cumulative.

During follow-up, for patients in the Treatment arm who have demonstrated hepatic progression with hepatic lesions amenable to TheraSphere, re-treatment with TheraSphere is allowed.

TheraSphere should be administered by appropriately trained or designated personnel from the departments of Radiology, Nuclear Medicine, and/or Interventional Radiology.

TheraSphere administration is generally considered to be an outpatient procedure in North America. It is generally considered to be an inpatient procedure in some countries in Europe. The physical location for after-care and recovery will be determined by individual institutional policies and facility configurations. The location and sequencing of treatment procedure may vary depending on the physical location of the angiography and nuclear medicine suites, the availability of portable gamma cameras, and the clinical judgment of the physician responsible for the treatment plan.

On the day of treatment, an arterial catheter will be placed percutaneously via the femoral or brachial artery under image guidance. The interventional radiologist performs this procedure. The patency of the catheter is maintained by an infusion of normal saline and a coagulation inhibitor (per institutional protocols) administered via a continuous infusion pump. Proper catheter positioning in the selected location in the hepatic artery will be verified on angiography before TheraSphere administration.

Standard medication protocol for sedation, pain and infection prophylaxis should be implemented per established institutional protocols. Prophylaxis with a gastric inhibitor (H2 blocker or proton pump inhibitor) is recommended to minimize risk of post-treatment gastrointestinal side effects. Although recommended for all patients undergoing treatment, this prophylaxis is especially important for patients undergoing TheraSphere treatment to the left lobe of the liver, due to the proximity of the gastrointestinal organs, and for patients with a prior history of peptic ulcer disease. Therapy should begin on the day of TheraSphere treatment and continue for 14-21 days following each TheraSphere treatment.

The TheraSphere labeling documents (Appendix 1) describes the specific procedure used to administer TheraSphere.

